**Note:**

- a:** Date of birth, Gender, Race;
- b:** Wound etiology/type, Duration, Anatomic location;
- c:** Pulse, Blood pressure, Respiration rate, Body temperature;
- d:** Red Blood Cell (RBC) count, White Blood Cell (WBC) count, Hemoglobin, Platelet;
- e:** Fibrinogen, Prothrombin Time (PT), Activated Partial Thromboplastin Time (APTT), International Normalized Ratio (INR);
- f:** Only for female subjects of reproductive potential;
- g:** Wound depth, edges, necrotic tissue type and amount, granulation tissue, undermining, exudate type and exudate amount;
- h:** Wound length, width, depth, area, and volume;

**1:** The visit will be conducted when subject is deemed ready for closure by investigator or treatment duration up to 14 Days (+/-1 Day).

**2:** For subjects withdrawing from the trial or discontinuation of trial treatment.

**3:** Definitive surgical debridement (if applicable)

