5.4. SAMPLE SIZE CALCULATION

The number of evaluable subjects required for this trial is 128 subjects (64 per treatment arm). To account for a potential 10% drop-out rate, at least 140 subjects (70 per treatment arm) will be randomly assigned in a 1:1 allocation ratio to V.A.C. VERAFL™ or control group.

140 evaluable subjects (70 per study arm) will achieve approximately 80% power to detect a difference with a non-inferiority margin of 20% based on a one-sided t test with a significance level of 0.025 and pooled standard deviation being 40%.

Due to the uncertainty in the actual variability and trying to limit the study size to those strictly needed, a sample size re-estimation will be performed after 50% evaluable subjects per arm (70 subjects total) have completed End of Treatment Visit. This number of subjects is expected to provide a sufficiently precise calculation of the variability in the actual study population.

The point estimate for the pooled standard deviation will be used for the sample size re-estimation. If the re-estimated sample size is greater than 140, the sample size may be increased up to a maximum of 200 subjects to provide sufficient power for this study. If the re-estimated sample size is less than 140, the sample size of the study is still 140.

Considering the actual drop-out rate during the clinical trial, the drop-out rate needs to be adjusted from the expected 10% to 25%. The sample size will increase by 30 subjects, to a total of maximum 170 subjects.

170 evaluable subjects (85 per study arm) will achieve approximately 80% power to detect a difference with a non-inferiority margin of 20% based on a one-sided t test with a significance level of 0.025 and pooled standard deviation being 40%.

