7.3. RETESTS, UNSCHEDULED VISITS AND EARLY TERMINATION DATA

In general, for by-visit summaries, data recorded at the nominal visit will be presented. Unscheduled measurements will not be included in by-visit summaries.

In the case of a retest (same visit number assigned), the last available measurement for that visit will be used for by-visit summaries.

Early termination data will be mapped to the next available visit number for by-visit summaries.

Listings will include scheduled, unscheduled, retest and early discontinuation data.

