Exudate amount	1 = None, dry wound 2 = Scant, wound moist but no observable exudate 3 = Small 4 = Moderate 5 = Large	

Evaluation time point: Day of Randomization (Day 0), Dressing Change Visit (s), End of Treatment Visit.

Statistical method: The descriptive statistics (frequency and percentage) of wound clinical assessments change from baseline (change scores from -4 to +4) will be summarized by treatment group, visit and overall. Listings will be presented and sorted by treatment group, subject id.

The Wilcoxon signed rank test and the Wilcoxon rank-sum test will be performed to detect significant changes from baseline within treatment group (p-values) or significant differences in change scores between treatment groups (p-values).

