15.5. SUMMARIES FOR NPWT APPLICATION

The application time (minutes) for each dressing change, any leaks and treatment settings will be listed and summarized by treatment group.

16. Exploratory endpoints

An exploratory analysis will be conducted on the exploratory endpoints (volume, area and granulation tissue) using the FAS. Listings will be presented and sorted by treatment group, subject id.

Repeated measure analysis of variance using mixed model on mean change in exploratory endpoints(volume, area and granulation tissue) at each dressing change time point as dependent

Analysis Plan

Protocol No.: KCI.VERAFLO.2018.02

variables with center, treatment group and treatment-by-center interaction as fixed factors, wound size (wounds surface area, $<15\text{cm}^2$ (ref), $15\text{-}30\text{cm}^2$, and $>30\text{cm}^2$) as covariate, and time point as repeated factor will be performed using mixed model. The P-value of center, treatment group, treatment-by-center interaction, wound size and time point will be reported. LS Means and LS Mean difference and P-values for LS Mean difference will be reported out for each visit.

Above statistical analysis method will be conducted on wound area.

An example of SAS code is provided:

```
Proc mixed DATA=xxx covtest metood=ml;
Class id treat center woundtype timepoint;
Model volume(or area,or granulation tissue)=treat center treat*center woundtype timepoint
/htype=3 s noint;
Repeated timepoint/type=sample (covariance structure may be TOFL, AR(1) or UN. Likelihood
ratio testing (LRT) may be used to select best fitting model
Subject=id(treat);
Run;
```

17. Evaluation of Safety

All outputs for safety outcomes will be based on safety set, and presented by treatment groups.

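### From the third dressing change on, dressing-change rows and the SAP Section 16 model leave out wounds at the moment they become ready, which pulls any true difference toward zero by an amount the documents cannot fix

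*SAP*

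**What the plan says.** **Where a ready wound's last reading goes.** Protocol 5.5.1, note 1, on the End of Treatment visit: "The visit will be conducted when subject is deemed ready for closure by investigator or treatment duration up to 14 Days (+/-1 Day". It is a visit of its own, separate from the dressing-change visits. SAP 6.1 counts a subject whose wound is deemed ready as having completed the study.

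**How visits are filed.** SAP 7.3 uses the nominal visit for by-visit summaries. For withdrawals it says: "Early termination data will be mapped to the next available visit number for by-visit summaries". SAP 7.4 rules out visit windowing. No rule gives a ready wound's End of Treatment reading a place in the dressing-change sequence.

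**Where it matters.** SAP Section 16 models volume, area and granulation tissue at the dressing-change time points and promises that "LS Means and LS Mean difference and P-values for LS Mean difference will be reported out for each visit". SAP 15.1.3 and 15.2.3 tabulate volume and area by visit. SAP 15.2.4 tabulates wound-score changes by visit and plans a rank-sum test for "significant differences in change scores between treatment groups (p-values", without naming the visit tested.

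**Timing.** Protocol 5.2.5 expects at least two dressing changes for every patient. Protocol 5.5.3 sets the interval at 48 to 72 hours in both arms.

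**The concern.** A wound judged ready at a dressing removal has its End of Treatment visit in place of a dressing-change visit. The reading that accompanied the judgement is then absent from that dressing-change row and from every later one. If readiness has anything to do with the quantity measured, the wounds that leave are the better ones, and the arm that prepares wounds faster loses more of them.

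The remaining comparison is conditional on not being ready. It tends to understate a real difference, whichever arm is better. A repeated-measures model does not fully correct this, because the missing value is itself related to why it is missing. Small late differences with unremarkable p-values could then be read as evidence of similarity in a trial whose aim is non-inferiority.

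**Working it through.** **1. The plan's own figure.** The documents give no number for the by-visit rule. The related figure is the sample size: "The number of evaluable subjects required for this trial is 128 subjects (64 per treatment arm", "based on a one-sided t test with a significance level of 0.025 and pooled standard deviation being 40" per cent, margin 20 per cent, 80% power.

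- Normal approximation: n per arm = 2(1.96 + 0.8416)² × 0.40² / 0.20² = 2 × 7.849 × 4 = 62.8, so 63.
- Noncentral t: 64 per arm, power 0.8015. The 128 is reproduced.

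It supplies the SD of 40 points and a 20-point scale for what follows.

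**2. When the gap opens.** With two dressing changes completed first, the earliest removal at which a wound can leave as ready is the third: 3 × 48 h = 6 days to 3 × 72 h = 9 days. Changes 1 and 2 then lose no ready wounds. The only readiness times in the documents (medians of 6 and 5 days, Protocol 3.1.3.1) come from a different study.

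**3. Mechanism in closed form, extreme case.** Let the arms be N(0,1) and N(0.5,1), and let a wound leave exactly when its score exceeds c. Then E[X | X < c] = μ − φ(c − μ)/Φ(c − μ).

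With half the control wounds gone, c = 0:

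- Control: −0.3989/0.5 = −0.798.
- Test: 0.5 − 0.3521/0.3085 = −0.641.
- Difference: 0.16 SD instead of 0.5.

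With 20% and 40% gone, the same formula gives 0.26 and 0.18. The losses are 49%, 63% and 69% at 20%, 40% and 50% gone. This treats readiness as a sharp cut on the very score compared, which the documents do not say.

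**4. Simulation over a range of links.** 400,000 wounds per arm. Assumptions not in the documents:

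- mean volume reduction rises linearly to 60% (control) and 80% (test) at day 14;
- 80% of the day-14 variance comes from a wound-level slope;
- changes fall at days 2.5, 5, 7.5, 10 and 12.5;
- half the control wounds are ready by day 7.5;
- b is the log-odds of readiness per 40 points of reduction;
- there are no withdrawals.

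The SD at day 14 is 40, as in the SAP. Results with the two-change minimum kept (differences in percentage points; shares kept come from unrounded values):

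| b | Change 3: still in, control/test | Change 3: true → seen (kept) | Change 5: still in, control/test | Change 5: true → seen (kept) |
|---|---|---|---|---|
| 0 | 50% / 50% | 10.7 → 10.6 (100%) | 12% / 12% | 17.8 → 17.7 (99%) |
| 1 | 50% / 44% | 10.7 → 10.0 (93%) | 11% / 7% | 17.9 → 13.8 (77%) |
| 2 | 50% / 40% | 10.7 → 8.5 (79%) | 13% / 6% | 17.9 → 9.1 (51%) |
| 4 | 50% / 36% | 10.7 → 6.1 (57%) | 16% / 7% | 17.8 → 5.7 (32%) |
| 8 | 50% / 33% | 10.8 → 4.4 (41%) | 18% / 8% | 17.8 → 4.3 (24%) |

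At changes 1 and 2 every row keeps 100%.

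**5. What restoring the reading does.** The model here has a treatment-by-visit term. Entries are the share of the true difference recovered, at change 3 / change 5.

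| b | Model without the readings | Model with them | Raw rows with them |
|---|---|---|---|
| 0 | 100% / 99% | 100% / 100% | 100% / 100% |
| 1 | 96% / 90% | 100% / 99% | 100% / 89% |
| 2 | 87% / 74% | 100% / 99% | 100% / 69% |
| 4 | 69% / 48% | 100% / 98% | 100% / 50% |
| 8 | 50% / 33% | 100% / 97% | 100% / 43% |

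Raw later rows improve but stay biased, because wounds ready at an earlier change are still absent. The model with the readings is close to unbiased throughout.

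**6. The sample code.** The model statement in SAP Section 16 has treatment, center, their interaction, wound size and time point, but no treatment-by-timepoint term. It cannot produce the separate difference per visit that the text promises.

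**The case against.** The strongest reply is that little of consequence is touched. The End of Treatment reading is not discarded: it has its own row and it is the basis of the primary endpoint (SAP 15.1.1). The area ANCOVA also uses the rate at readiness or day 14. The by-visit volume and area tables are descriptive, and Section 16 is labelled exploratory. Continuous summaries already print n, Kaplan-Meier and log-rank methods analyse readiness directly, and imputed area is also tabulated by visit. All of this stands. It limits the importance of the point but does not supply the missing filing rule.

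Several stronger readings are tempting and do not hold:

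- **Every dressing-change comparison is affected.** Not if the Protocol 5.2.5 minimum is followed; changes 1 and 2 are then complete for ready wounds.
- **Most of a true difference is lost.** That needs a strong link. Readiness is the investigator's judgement, and Protocol 5.3.1.1 bars use of the 3D images to guide treatment, so the link with measured volume may be weak.
- **Withdrawn wounds are carried into dressing-change rows.** The next available visit number is undefined and could be End of Treatment. The mapping is also stated only for by-visit summaries, not for the model.
- **Between-arm wound-score tests are run at each visit.** In SAP 15.2.4 the word visit belongs to the descriptive tables; the test sentence names none.
- **The non-inferiority result is favoured.** The primary test does not use these rows, and the shrinkage would equally hide an advantage of the investigational device.

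**Conclusion.** The gap is real and limited to the dressing-change rows and the Section 16 model. From change 3, given the two-change minimum, these compare only wounds not yet ready, plus possibly withdrawn ones.

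The loss in the raw rows is essentially nil if readiness is unrelated to the measurement. It is 7% at change 3 and 23% at change 5 for a weak link (b = 1), 21% and 49% for a moderate one (b = 2), and 43% to 59% and 68% to 76% for strong ones (b = 4 and 8). The model as specified for input loses less but is not protected: it misses 4% to 50% at change 3 across b = 1 to 8, even with the interaction term it currently lacks.

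These figures rest on the assumed trajectories, readiness timing and link. The documents do not give the link, so no single figure can be claimed. The point deserves a correction because per-visit p-values are planned and the data needed are already collected. It does not put the primary conclusion at risk.

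**What to change.** - **SAP Section 16:** enter a ready wound's End of Treatment reading once, under the dressing-change number at which it was taken, and not again as a separate time point. Add the treatment-by-timepoint term to text and code.
- **SAP 7.3:** apply the same assignment in the by-visit volume, area and wound-assessment tables. Define the next available visit number, including whether it can be End of Treatment.
- **By-visit tables:** print the number of wounds contributing per arm at each change, and note that raw later rows remain conditional on not yet being ready.
- **SAP 15.2.4:** state that the between-arm Wilcoxon test uses the End of Treatment change score.

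The cost is SAP wording and a small programming rule, with no new data. If by-visit Wilcoxon tests were intended, there will be fewer p-values.

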7.4. WINDOWING CONVENTIONS

No visit windowing will be performed for this study

7.5. STATISTICAL TESTS

The descriptive statistics of continuous variables include number, mean, standard deviation, median, minimum and maximum. Frequency and percentage will be used in the descriptive statistics for categorical variables. Unless otherwise specified, all statistical tests will be performed at a significance level of 5.0% (two-sided) with two-sided 95% confidence interval (CI).

7.6. COMMON CALCULATIONS

For quantitative measurements, change from baseline will be calculated as:

- Test Value at Treatment Interval X – Baseline Value

7.7. SOFTWARE VERSION

All analyses will be conducted using SAS version 9.2 or higher.

8. Output Presentations

The templates provided with this SAP describe the presentations for this study and therefore the format and content of the summary tables, figures and listings to be provided by Kun Tuo Biostatistics. All data collected will be listed. When the content of this SAP does not match the template, the template will take priority.

9. Disposition and Withdrawals

All subjects who provide informed consent will be accounted for in this study.

The numbers and percentages of subjects who were randomized, completed and discontinued the study early, as well as the reasons for incompletion, will be summarized by site treatment and overall. The numbers and percentages subjects in each analysis set will be provided by treatment group and overall.

Disposition of all subjects will be listed.

10. Protocol Deviations

Any act of intentional or unintentional variation of the protocol is defined as protocol deviation (PD). The information of protocol deviation was recorded on the “protocol deviation” CRF page.

Protocol deviations will be summarized by treatment, categories and overall.

The following information will be reported in Full Analysis Set:

- Frequency and percentage of randomized patients with at least one protocol deviation/violation will be summarized by treatment and overall.
- Protocol deviation will be summarized by grade of deviation, treatment group and overall.
- Detailed information of protocol deviations will be listed, including PPS inclusion/exclusion status.

11. Demographic and other Baseline Characteristics

Demographic data and other baseline characteristics will be presented for Full Analysis Set and the Per Protocol Set.

Demographic data and other baseline characteristics will be summarized by treatment and categories, listing will be provided, including PPS inclusion/exclusion status.

Statistical testing will be carried out for demographic or other baseline characteristics (Fisher's

exact for nominal or ordinal variables, ANOVA for continuous variables).

The following demographic characteristics will be reported for this study:

- Age (years) = (date of consent - date of birth+1)/365.25, and result is rounded down to the nearest integer
- Gender
- Child-bearing potential
- Race
- Ethnicity
- Definitive Surgical Debridement
- Baseline wound area
- Baseline wound area group based on randomization strata (<15cm², 15-30cm², and > 30cm²)
- Baseline wound volume
- Baseline wound history (wound etiology/type, location, wound age(date of consent - date of wound onset) at the time of consent)

12. Medical History/Wound History

Medical history/Wound History information will be presented for safety set.

The information of medical history inquiry is recorded on the “Medical History Inquiry” CRF page and will be listed and summarized by treatment group and overall.

The following information will be reported for this study:

- Any medical history in the last 3 months(yes/no)
- Serious diabetes medical history(yes/no)
- Surgical history(yes/no)
- Any known allergy in the last 3 months(yes/no)

Pre-existing medical conditions are recorded on the “Medical History” CRF page.

- Medical History will be coded using MedDRA version 22.0.
- Medical History will be listed and summarized by system organ class (SOC) and preferred term (PT).
- If a subject had more than one medical history within a system organ class or Preferred Term, the subject will be counted only once within a system organ class or Preferred Term.

- Medical History conditions are defined as those conditions which stop prior to or at baseline.

Wound history conditions are recorded on the "Wound History" CRF page.

- Wound History for wounds selected for this study will be listed and summarized by wound etiology/type, location, wound age(date of consent - date of wound onset) at the time of consent, Ongoing(Yes/No), Any treatment(Yes/No) and Wound Treatment.
- Wound History conditions are defined as those conditions which stop prior to or at baseline.

13. Medications

Prior and concomitant medications will be presented for safety set, and coded using WHO-Drug DDEB3 201903..

- Concomitant medication will be listed and summarized by Anatomical Therapeutic Chemical (ATC) level 3 and preferred term, a listing will be presented for prior medication. If a subject had more than one concomitant medication within ATC, the subject will be counted only once within a ATC Term.
- Prior medications are medications that started and stopped prior to the first application of study device within the observation.
- Concomitant medications are medications which:
 - Started prior to, on or after the first application of study device within the observation and started no later than the end of the study;
 - AND ended on or after the date of first application of study device within the observation or were ongoing at the end of the study

14. Procedures

The information (frequency and percentage) of prior and concomitant procedures will be summarized by indication, treatment group and overall. When the indication is "AE" or "MH", the indication will be summarized by SOC and PT.

- Prior procedures are procedures which started and stopped prior to the first application of study device within the observation.
- Concomitant Procedures are Procedures which:
 - Started prior to, on or after the first application of study device within the observation and started no later than the end of the study;
 - AND ended on or after the date of first application of study device within the observation or were ongoing at the end of the study

15. Efficacy Outcomes

PPS is the primary analysis data set for efficacy evaluation. FAS is the secondary analysis set for efficacy evaluation.

15.1. PRIMARY EFFICACY

15.1.1. PRIMARY EFFICACY VARIABLES & DERIVATIONS

Primary efficacy endpoints

The primary efficacy variable is Wound Volume Reduction Rate, which is wound volume change over 14 days or until deemed ready for closure by investigator (whichever occurred first) ;

Derivations of analysis variables

wound volume reduction rate (unit: %) = (wound volume before initial study treatment –wound volume after study treatment 14 days or deemed ready for closure before 14 days)÷wound volume before initial study treatment×100%.

Data of the variables above will be collected from the CRF.

15.1.2. MISSING DATA METHODS FOR PRIMARY EFFICACY VARIABLES

Subjects in the study whose wound volume reduction rate at effective visit (after study treatment 14 days or deemed ready for closure before 14 days) is unknown will have these missing values imputed in the FAS. Subjects in the PPS will not have any missing values.

The multiple imputation (MI) method will be used to calculate the primary endpoints for each subject for the FAS. The last observation carried forward (LOCF) method and next observation carried back (NOCB) method for missing volume measures will be used to calculate the primary endpoints for each subject for sensitivity analysis using the FAS.

15.1.3. PRIMARY ANALYSIS OF PRIMARY EFFICACY VARIABLES

PPS population is the primary efficacy analysis population. Descriptive statistics of actual wound volume, wound volume changes (wound volume before study treatment –wound volume of each visit) and wound volume reduction rate at visit (wound volume before initial study treatment –wound volume at visit)÷wound volume before initial study treatment×100% by visits, treatment group and overall will be provided.

Listings of actual wound volume will be presented and sorted by subject id, treatment group and visit.

The statistical hypothesis for testing the treatment group difference for primary efficacy endpoint is presented as follows:

- $H_0: M_T - M_C \leq -0.20$ tested against the alternative hypothesis
- $H_1: M_T - M_C > -0.20$

where:

M_C is the means in control group and M_T is the means in to V.A.C. VERAFLTM group.

A two-sided 95% confidence interval for $M_T - M_C$ will be constructed using the method of ANCOVA with treatment group, center, and treatment-by-center interaction (if the interaction effect is not statistically significant, then it will be removed from the final model) as fixed factors, and wound size (wounds surface area, <15cm² (ref) , 15-30cm², and >30cm²) as covariate.

The following statistics will be presented: LS Means, difference of the LS Means as well as its two-sided 95% CI, p-value for LS Mean difference. If the lower limit of the two-sided 95% confidence interval of difference is greater than -0.20, then it will be concluded that the V.A.C. VeraFloTM Dressing Kit is non-inferior to the approved control dressing in China (Local) + wall suction.

A rejection of the null hypothesis will trigger superiority testing based upon treatment difference. If the lower limit of the CI is greater than zero, V.A.C. VERAFLTM Dressing Kit is proven to be superior to control dressing.

The two hypothesis tests are hierarchically structured so that the second test (superiority) will only be considered if the first test (non-inferiority) is rejected. There is no alpha adjustment for the second test

as a result of the hierarchical testing.

Furthermore, the following statistics will be presented: P-value of treatment group, center, wound size, and treatment-by-center interaction (present only if interaction effect is significant). If the treatment-by-center interaction in ANCOVA model is significant (<0.025), it always reveals that there is the heterogeneity of substantial treatment in different centers. In order to explain the heterogeneity influence for reliability of statistical conclusion, the descriptive statistics will be reported by different centers.

An example of SAS code is provided:

```
Proc glm;
Class treat woundtypecenter;
Model wound volume reduction rate=treat center treat*center woundtype/ss3;
Lsmean treat/cl pdiff tdiff;
run;
```

